## **11. SAFETY AND EFFECTIVENESS ASSESSMENTS**

Safety assessment procedures are barely applicable to the current study since widely consumed food ingredients will be used for the study. Volunteers with intolerance or adverse reaction to phospholipids or lycopene will not be enrolled in the study.

Effectiveness assessment will be performed by measuring liver size and serum lipid levels at the intermediate and final points of the interventional period.

### **11.1 Safety assessments**

The volunteers will be instructed to check for the appearance of skin rash, nausea and dyspepsia and to report any of these to the Medical Officer should they occur.

### **11.2 Effectiveness assessments**

Computed tomography, measurements of blood pressure, serum activities of liver specific enzymes and concentration of total cholesterol, LDL, HDL and triglycerides will be measured as effectiveness assessment parameters.

## **12. ADVERSE EVENT REPORTING**

Occurrence of adverse events in subjects consuming lycopene and phosphatidylcholine is very unlikely. If any do occur it is the responsibility of the Medical Officer and the PI to determine and analyze adverse event cause.

Among adverse reactions could be skin rash, dyspepsia and nausea.

Occurrence of any of these will be considered as a reason for volunteer withdrawal from study participation.

### **12.1 Recording/Reporting requirements**

All subjects will be required to report any possible adverse effect to the Medical Officer assigned to the study, whose responsibility is to immediately inform the PI of any possible adverse reaction. Moreover, appropriate information will be immediately passed to the Local Ethical Committee. All observed or volunteered adverse events (serious or non-serious) and abnormal test findings, regardless of study group or suspected causal relationship to the study, will be recorded in the subjects' case histories. Adverse events or abnormal test findings felt to be associated with the study will be followed up until the event (or its sequelae) or the abnormal test finding resolves or stabilizes.

For all adverse events, sufficient information will be pursued and/or obtained so as to permit 1) an adequate determination of the outcome of the event (i.e., whether the event should be classified as a *serious adverse event*) and; 2) an assessment of the causal relationship between the adverse event and the study product(s).

An abnormal test finding will be classified as an *adverse event* if one or more of the following criteria are met:

- The test finding is accompanied by clinical symptoms
- The test finding necessitates additional diagnostic evaluation(s) or medical/surgical intervention; including significant additional concomitant drug treatment or other therapy

Lycotec Ltd and Saratov Institute of Cardiology will promptly review documented adverse events and abnormal test findings to determine 1) if the abnormal test finding should be classified as an adverse event; 2) if there is a reasonable possibility that the adverse event was caused by the study product(s); and 3) if the adverse event meets the criteria for a *serious adverse event*.

If the final determination of causality is "unknown and of questionable relationship to the study product(s)", the adverse event will be classified as *associated with the use of the study product* for reporting purposes. If the Sponsor-Investigator's final determination of causality is "unknown but not related to the study product", this determination and the rationale for the determination will be documented in the respective subject's case history.

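### Adverse events have a stated follow-up to an outcome only if thought linked to the study, and the protocol does not settle who judges that link or whether they are blinded

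*Protocol*

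**What the plan says.** **Recording.** Protocol Section 12.1 is broad: "All observed or volunteered adverse events (serious or non-serious) and abnormal test findings, regardless of study group or suspected causal relationship to the study" are entered in the case histories.

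**Follow-up.** The same paragraph then narrows: "Adverse events or abnormal test findings felt to be associated with the study will be followed up until the event (or its sequelae". The sentence goes on to resolution or stabilisation. It does not say whose opinion decides.

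**Information on all events.** The next paragraph begins "For all adverse events, sufficient information will be pursued and/or obtained so as to permit 1) an adequate determination of the outcome". A bracket after it explains outcome as whether the event is to be classed as serious. The second item is causal relationship.

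**Who judges cause.**
- Section 12, on the Medical Officer and PI: "it is the responsibility of the Medical Officer and the PI to determine and analyze adverse event cause".
- Section 12.1, on the developer and the site: "Lycotec Ltd and Saratov Institute of Cardiology will promptly review documented adverse events and abnormal test findings". Their questions include causality. Section 7.4.6 identifies Lycotec Ltd as the developer of the lycopene formulation.
- Section 12.1, closing paragraph: the final call on causality is described as the Sponsor-Investigator's.

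**Unknown cause.** Where the relationship is doubtful, Section 12.1 classes the event as product-associated for reporting. Where the finding is "unknown but not related to the study product", the determination and its rationale go into the case history.

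**Withdrawal.** Section 12.2 withdraws and replaces any subject with an adverse reaction or abnormal laboratory findings, with a report to the ethics committee. It sets no causality condition on the laboratory findings.

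**Blinding.** The Protocol Summary says in one place that no trial personnel will know group assignment, and shortly afterwards that the PI alone will know it.

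**The concern.** Whether an abnormality persists or settles after product is stopped is useful evidence on its cause. Under Section 12.1 that evidence is assured only where someone has already decided that the event is linked to the study. A correct call of association can be confirmed, but a mistaken call of no association may never be tested.

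This matters in NASH because a rise in liver tests has a ready alternative explanation in the disease itself. Section 12 also states an expectation in advance: "Occurrence of adverse events in subjects consuming lycopene and phosphatidylcholine is very unlikely". A judgement that opens or closes follow-up should therefore be clearly assigned and made blind to allocation. The protocol secures neither. At stake are the completeness of the safety data and their freedom from bias, not the primary endpoint.

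**Working it through.** No arithmetic applies. The protocol gives no expected event rate, and its total is 40 in the Protocol Summary but 80 in Section 13.2, so even the denominator is unsettled. The check is to set the rules side by side.

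**Step 1: what each class of event is assured under Section 12.1**

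| Event | Recorded | Seriousness and causality pursued (all-events sentence) | Observed to resolution or stabilisation |
|---|---|---|---|
| Adverse event thought linked to the study | Yes | Yes | Yes |
| Adverse event thought not linked | Yes | Yes | Not stated |
| Abnormal finding below the adverse-event criteria, thought linked | Yes | Not stated | Yes |
| Abnormal finding below those criteria, thought not linked | Yes | Not stated | Not stated |

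The all-events sentence does not fill the last column, because its bracket ties outcome to seriousness and not to how the event ended. It also speaks of adverse events, so it does not reach abnormal findings that fall short of that class.

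**Step 2: can scheduled visits supply the outcome?** For a retained subject, yes. Liver enzymes are effectiveness measures (Section 11.2) and are repeated at later visits. But Section 12.2 withdraws a subject with abnormal laboratory findings and brings in a replacement, and no visits are described for a withdrawn subject. For that subject the conditional sentence in Section 12.1 is the only stated route to later observation.

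**Step 3: follow one case through.** A subject's liver tests rise at an intermediate visit and the rise is attributed to underlying NASH.
1. It is recorded (12.1).
2. The subject is withdrawn and replaced, and a report is filed (12.2).
3. The finding is not thought linked to the study, so the follow-up sentence does not apply (12.1).
4. The default for doubtful relationship need not apply either, because a cause has been assigned.

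The result is a recorded event with no stated route to an outcome.

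**Step 4: who decides at point 3?** The follow-up sentence names nobody. Causality appears with three sets of assessors: the Medical Officer and PI; Lycotec Ltd with the Institute; and the Sponsor-Investigator. No order is given, and no rule for disagreement.

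**Step 5: are they blinded?** The PI is an assessor under Section 12. One statement in the Protocol Summary has the PI knowing each subject's group; another has no trial personnel knowing it. Both cannot hold. If the first governs, at least one causality assessor is unblinded.

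**The case against.** Several points on the other side are sound.

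- **Events are not dropped.** A reader might infer that liver events blamed on NASH disappear. The text does not support this. They are recorded whatever the suspected cause, and seriousness and causality information is sought for every adverse event. A between-arm comparison of all recorded events survives a mistaken attribution. Only a stated follow-up to an outcome is missing.
- **The two categories of unknown cause do not contradict each other.** A reader might infer that one unknown event can be counted or removed by choice of phrase. They are different conclusions. In one the product's role is in doubt and the default is association; in the other the product is judged not responsible and a rationale must be documented.
- **The developer has no stated power to downgrade a call.** It reviews jointly with the Institute, and the final call is the Sponsor-Investigator's. A downward bias in product-associated events is a possibility, not something the documents show.
- **The assessors may be sequential:** site analysis, joint review, final determination. The Sponsor-Investigator may also be the PI, although Section 17.2 speaks of Sponsor and Investigator as agreeing parties. Parts of the key-roles section were removed from the text available here and may clarify this. The order is still not stated in Sections 12 and 12.1, where the rule operates.
- **The trigger is association with the study,** which is wider than association with the product. That softens the condition but leaves it subjective and unassigned.
- **It is withdrawal under Section 12.2 that ends observation, whatever the cause.** This is right. It is also why the condition in Section 12.1 matters: after withdrawal nothing else is stated.

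**Conclusion.** The point holds in a limited form. Follow-up to resolution or stabilisation is stated only for events thought linked to the study. The person who decides on that link is not named, causality is spread over parties whose relation is not set out, and the protocol contradicts itself on whether one of them is blinded. Evidence that could overturn a mistaken unrelated call is therefore assured only for events where no such call was made.

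No numerical size can be given from the documents. The matter is a modest weakness in the safety data and does not affect an efficacy analysis. It is fixed in the protocol's own wording, so it is not something left to a separate analysis plan.

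The conclusion rests on three readings: silence on unassociated events means that no follow-up is planned for them; a rise in liver tests counts as an abnormal laboratory finding under Section 12.2; and withdrawal from the study ends scheduled visits.

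**What to change.** 1. **Section 12.1, follow-up.** Remove the causality condition. Every adverse event or abnormal finding still open at withdrawal or at the last visit is observed until it resolves or stabilises, whatever its attributed cause.
2. **Sections 12 and 12.1, causality.** Reconcile the assessors to one named role, blinded to allocation, for the initial call. Later reviews by the developer, the Institute or the Sponsor-Investigator are recorded alongside that call and do not replace it.
3. **Protocol Summary, blinding.** Reconcile the two statements on whether the PI knows allocation.
4. **Leave the category for unknown cause judged unrelated as it is,** with its documented rationale. Deleting it would label as product-associated some events for which the product was judged not responsible.

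The cost is a change of wording and a few repeat contacts or routine tests in subjects with open events.

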## **12.2 Withdrawal of subjects due to adverse events**

Any subject with an adverse reaction and/or abnormal laboratory test findings will be withdrawn from the study by the Medical Officer and replaced with an eligible volunteer from the pre-screened pool of volunteers. An appropriate report to the Local Ethical Committee will be filed.

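### A symptom-free liver-test rise whose only consequence is withdrawal is an adverse-event withdrawal under section 12.2 of the protocol but not an adverse event under section 12.1

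*Protocol*

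**What the plan says.** Protocol section 12.1 gives the rule for when an abnormal test becomes an adverse event. It applies "if one or more of the following criteria are met", and two criteria follow:

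- The first concerns symptoms: "The test finding is accompanied by clinical symptoms".
- The second does not depend on symptoms and looks at what has to be done next: "The test finding necessitates additional diagnostic evaluation(s) or medical/surgical intervention; including significant additional concomitant drug treatment or other therapy".

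Section 12.1 also has every abnormal finding entered in the case history, whatever the group or suspected cause. The company that developed the formulation and the institute then review each one to decide whether it is an adverse event.

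Section 12.2 carries the heading "Withdrawal of subjects due to adverse events". Its rule is: "Any subject with an adverse reaction and/or abnormal laboratory test findings will be withdrawn from the study by the Medical Officer". The subject is replaced from the pre-screened pool, and a report goes to the local ethics committee.

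The safety section does little to fill in the picture. Section 11.1 has volunteers "instructed to check for the appearance of skin rash, nausea and dyspepsia" and names no laboratory test. Section 11.2 lists "serum activities of liver specific enzymes" among the effectiveness measures only. The Protocol Summary (Study Design) shows that ALT, AST, alkaline phosphatase, GGT and total bilirubin are measured at the check-ups.

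**The concern.** The two sections deal with the same event and classify it differently. Section 12.2 treats an abnormal laboratory finding as reason enough to end participation and places that under adverse events. Section 12.1 decides what an adverse event is, and its criteria do not include ending participation. A finding can therefore have the most serious consequence the protocol provides for a subject and still not enter the adverse-event count.

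The liver is the diseased organ here, and its tests are drawn at scheduled visits, so a rise can come to light without any symptom. If such rises lead to withdrawal and nothing else, an arm could report few or no hepatic adverse events although subjects left it because of their liver tests. Replacement adds to this, because the arm is refilled and the completed group looks intact. The safety conclusion would then lean towards no harm.

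**Working it through.** The protocol gives no figure on this point, so there is none to reproduce. The check is to run each kind of abnormal laboratory finding through both sections.

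**Inputs.** From 12.1: two criteria, either of which is enough. From 12.2: withdrawal for abnormal laboratory findings, with no threshold, no symptom condition and no reference to baseline.

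| Symptoms | Further evaluation or treatment needed | 12.1: adverse event? | 12.2: withdrawn? |
|---|---|---|---|
| Yes | Yes or no | Yes, first criterion | Yes |
| No | Yes | Yes, second criterion | Yes |
| No | No | Neither criterion met | Yes |

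The sections agree in the first two rows and part in the third. The gap is that one row.

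**Can the third row occur?** Yes. Removal under 12.2 can be the whole response to the finding, and then nothing remains to meet the second criterion.

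**A related difficulty in 12.2.** Section 7.4.4 enrols patients whose NASH is definite or probable on computed tomography and laboratory tests. Abnormal values at entry are therefore foreseeable. Section 12.2 does not say whether a value already abnormal at Day 0 counts. Any new adverse-event criterion tied to withdrawal inherits this problem unless it is anchored to Day 0.

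**Size per case.** The planned arm is 20 in the Protocol Summary (Sample Size) and 40 in section 13.2.

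- Without allowing for replacement, one case is 1/20 = 5% or 1/40 = 2.5% of an arm.
- Replacement raises the number exposed. If *k* subjects are withdrawn and replaced in an arm filled to *n*, then *n + k* received product and the uncounted share is *k*/(*n + k*). For *k* = 1 this is 1/21 = 4.8% or 1/41 = 2.4%.

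The documents give no basis for choosing *k*, so only the size per case can be stated.

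**The case against.** Several points on the other side are sound, and they limit the finding.

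- **Symptom-free findings are not left out in general.** A reader who stops at the first criterion might infer that they are. The second criterion needs no symptoms, so a silent rise that is worked up or treated is an adverse event.
- **Follow-up may narrow the gap.** Section 12.1 follows findings thought to be related to the study until they resolve or stabilise. Following an enzyme rise means repeat tests, which could be read as further diagnostic evaluation. On that reading the gap is mainly rises judged unrelated. The text does not say so, and the point stands for those.
- **There are safeguards.** Findings are recorded, reviewed and reported to the ethics committee after withdrawal. Section 12.1 also says when a finding *will* be an adverse event, not that nothing else can be, so the review could go further. But it is given no other criterion, so going further is a matter of discretion. Local visibility does not make a finding an adverse event.
- **The rise need not vanish from all results.** A reader might infer that it appears in neither safety nor effectiveness data. That is not established. Intermediate laboratory values are scheduled (section 7.4.2), section 11 assesses effectiveness at intermediate points too, and safety tables may be set out in a statistical analysis plan that is not shown.
- **The food-ingredient rationale is not a contradiction.** Section 11 says "Safety assessment procedures are barely applicable to the current study since widely consumed food ingredients will be used for the study". A reader might set this against the claims of hepatic delivery and enhanced bioavailability in sections 7.2 and 7.4.6. Those claims are an argument against the rationale. They do not contradict a statement about ingredients, and section 7.2 itself describes the ingredients as food-derived.
- **No headline incidence follows.** Someone might assume 3 silent withdrawals in 20, call the true rate 15%, and compare it with the one-sided 95% upper bound for 0/20, which is 1 − 0.05^(1/20) = 13.9%. The count is invented, and replacement makes the rate 3/23 = 13.0%, below that bound. Against 0/23 the bound is 1 − 0.05^(1/23) = 12.2%, so the order returns by less than one point. The comparison cannot carry weight.

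**Conclusion.** The point holds in a narrow form. A laboratory finding that triggers withdrawal under 12.2, without symptoms and without further evaluation or treatment, is placed among adverse-event withdrawals by 12.2 and is not an adverse event by the criteria of 12.1. Recording, review and the ethics-committee report leave that classification unchanged. Adverse-event counts by arm can therefore understate hepatic findings, by up to 5 points per case in an arm of 20 or 2.5 points in an arm of 40, and slightly less once replacements are counted among the exposed.

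This rests on two assumptions: that the reviewers apply the two stated criteria and no others, and that withdrawal is sometimes the only action taken. How often that happens cannot be estimated from the protocol. If it happened equally often in both arms, the comparison between arms would suffer less than the absolute rates. The matter belongs in the protocol, because an analysis plan tabulates adverse events as classified and would not by itself change the classification. It should be corrected, but it does not undermine the trial as a whole.

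**What to change.** 1. **Section 12.1:** add that an abnormal test finding that has worsened from the Day 0 value and leads to withdrawal is classed as an adverse event. The Day 0 anchor keeps pre-existing disease from being counted as an adverse event.
2. **Section 12.2:** the sponsor should reconcile what counts as an abnormal laboratory finding with section 7.4.4, which enrols patients partly on laboratory tests for NASH. Which withdrawal rule is right is a clinical matter for the sponsor. The request here is only that the sections agree.
3. **Section 11.1:** list ALT, AST, GGT, alkaline phosphatase and total bilirubin, all already measured, as safety measures as well as effectiveness measures.
4. **Reporting:** show worsening from Day 0 by arm for all subjects who received product, including those withdrawn and replaced, with their last value before withdrawal.

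The cost is protocol wording and one table from data already collected. The downside is a somewhat higher reported adverse-event count.

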## **12.2 Withdrawal of subjects due to adverse events**

Any subject with an adverse reaction and/or abnormal laboratory test findings will be withdrawn from the study by the Medical Officer and replaced with an eligible volunteer from the pre-screened pool of volunteers. An appropriate report to the Local Ethical Committee will be filed.

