**Study Design**

The study is designed as a double-blinded, interventional, randomized clinical study involving patients with NASH. A major research question is whether ingestion of lycopene stabilized with Lycosome™ formulated phosphatidylcholine chaperone can reverse clinical and laboratory manifestations of NASH. Therefore, the primary endpoint of the project is the size of the liver and parameters reflecting lipid accumulation in the hepatic tissue at the end of the interventional period. Changes in the activity of liver-specific enzymes and parameters of lipid homeostasis represent the secondary question since normalization of serum levels of hepatic enzymes represents another important criterion of liver damage and its reversal in NASH. Biochemical parameters in serum specimens will be investigated before commencing the study, at the intermediate time points of 1 month and in the end of the study after 2 months treatment. To assess changed in the liver span Ultrasonography was used before and in the end of the trial.

Subjects will be assigned to take orally once a day either capsules containing 450 mg of regular phosphatidylcholine or 450 mg of the same phospholipid in Lycosome™ formulation with 7 mg of lycopene (Cambridge, UK).

The formulations will be dispensed to the subjects during follow-up visits each month. Monthly visits are planned to determine compliance and adherence to the protocol. A basic medical check-up will be performed and subjects will be asked questions to determine adherence to the protocol during each visit.

Packaging and labeling of the study products will be carried out according to the guidelines of NIH and US Department of Health and Human Services as recommended for biologics and investigational health food products. The formulations will be shipped to the study site in specially designed containers with primary and secondary components. The container closure system will prevent exposure of the investigational products to light, moisture, temperature extremes and air. This packaging system guarantees stability of the product for intended use. Protection from microbial contamination will be provided by maintaining container integrity after the packaging system is sealed. An adequate and validated procedure was used for investigational product manufacture and packaging.

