All individual packages will be labeled with a numerical code. None of the volunteers or trial personnel will be informed of study group assignment for the duration of the study. Unblinding of the results is planned to be performed by an independent statistician who will be hired and assigned to the work at the end of the study period.

Upon arrival at the clinical site the study products will be inspected by the Medical Officer and Clinical Monitor, then placed in a locked room at the clinic. Only the Medical Officer, PI and Clinical Monitor will have access to the products during the study period. Each subject will be given a one month supply of the study product at the "zero" time point of the study and then subsequently for each month of the study period following verification of compliance with the study protocol.

Total study duration is six months with a medical check-up for each volunteer at the "0" time point of the study as well as at 1st month and at the 2nd, the end of the interventional period.

During the medical check-ups each volunteer will be subjected to thorough clinical and laboratory investigation. Clinical investigation will include reading the vital signs, determination of body mass index, anthropometry, blood pressure measurement and computed tomography (at the initial and final time points of the study). Among laboratory tests will be determination of fasting serum glucose and lipids (total cholesterol, LDL, HDL and total triglyceride

[figure not shown]

levels), determination of ALT and AST levels, alkaline phosphatase, gamma glutamyl transpeptidase, lactate dehydrogenase, total bilirubin, CRP, LDL oxidation and IOD. Moreover, serum lycopene concentration and lycopene isomer profile will be measured at the initial and final points of the interventional period. All volunteers will also be subject to a standard hematological investigation.

Results collected for each volunteer will be stored as both paper files and digital files in Excel format and will be available for access by the Medical Officer, Medical Monitor and PI. To avoid any bias each subject will be given a random computer code containing three numerical characters and three letters. Decoding of the individual results will be carried out by an independent statistician hired for the purpose.

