#### **7.4.2 Schedule of Procedures/Evaluations**

1. 2 months prior to study initiation. (Initial enrolment with preliminary physical and laboratory investigation).
2. 2 – 5 days prior to study initiation. Final qualifying physical and laboratory investigation.
3. Day "0" of the study. Physical and laboratory investigation to obtain baseline clinical and laboratory values. Computed tomography.
4. End of the 2nd and 4th months of the study. Physical and laboratory investigation to obtain mid-point clinical and laboratory values.
5. End of the 6th month of the study. Concluding physical and laboratory investigation to obtain final clinical and laboratory values. Computed tomography.

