## **9. STUDY DRUG COMPLIANCE AND ADHERANCE**

Compliance of subjects with the protocol and adherence to product intake will be determined by asking questions of the patients during intermediate and final visits to the clinical site and by random private telephone calls. Subjects with poor adherence to the study protocol will be withdrawn from the study by the Medical Officer.

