## **17. STUDY DISCONTINUATION CRITERIA**

### **17.1 Discontinuation of individual research subjects**

Individual research subjects can be withdrawn from the study due to occurrence of adverse effects, volunteer's request (regardless of reason) and non-compliance with the protocol. Volunteers withdrawn from the study will be replaced from the pre-screened pool of volunteers.

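### Randomised subjects withdrawn for adverse reactions, abnormal laboratory findings or poor adherence are replaced and have no planned final imaging, so end-of-period data come from subjects selected after randomisation

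*Protocol*

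**What the plan says.** Four sections of the protocol deal with withdrawal, and they differ in force.

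- Section 12.2 is mandatory: "Any subject with an adverse reaction and/or abnormal laboratory test findings will be withdrawn from the study by the Medical Officer and replaced". The replacement is an eligible volunteer from the pre-screened pool.
- Section 9 is also mandatory: "Subjects with poor adherence to the study protocol will be withdrawn from the study by the Medical Officer". Adherence is judged by questions at visits and by telephone calls, with no cut-off.
- Section 12 is permissive. It names rash, dyspepsia and nausea and adds: "Occurrence of any of these will be considered as a reason for volunteer withdrawal from study participation".
- Section 17.1 says that subjects can be withdrawn for adverse effects, at their own request or for non-compliance. Replacement is then the rule: "Volunteers withdrawn from the study will be replaced from the pre-screened pool of volunteers".

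On outcome measurement, the Study Design part of section 6 says that "the primary endpoint of the project is the size of the liver and parameters reflecting lipid accumulation in the hepatic tissue at the end", meaning when treatment closes. It schedules "computed tomography (at the initial and final time points of the study"), and it has ultrasonography of liver span before and at the end of the trial. Section 7.4.2 places tomography on day 0 and again at the last visit: "Concluding physical and laboratory investigation to obtain final clinical and laboratory values. Computed tomography". Section 11 mentions liver size at intermediate points, but neither schedule contains imaging there.

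The only follow-up stated after an event is in section 12.1. Events or findings thought to be associated with the study "will be followed up until the event (or its sequelae) or the abnormal test finding resolves or stabilizes".

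**The concern.** Randomisation makes the arms comparable at entry. That comparability carries through to the end only if outcomes are collected on everyone randomised, or if those lost are unrelated to arm and outcome. Here the protocol ends participation because of tolerability, laboratory values or adherence, all of which are observed after randomisation and may be related to outcome. It then fills the place with someone else. Replacement restores the head count but not the randomised comparison.

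This is a matter of conduct and cannot be left to an analysis plan. Such a plan can name an intention-to-treat set, but it cannot supply a final scan that was never taken.

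A smaller wording problem sits in the same sentence of 12.2. The laboratory trigger has no grade, threshold or causality condition. It does not refer to the section 12.1 criteria for when a test finding counts as an adverse event, and 17.1 does not list it as a reason. As worded it covers the liver enzymes and lipids that section 11.2 uses as effectiveness measures, in patients whose diagnosis rests partly on laboratory tests (section 7.4.4).

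**Working it through.** **Step 1: what happens to a subject withdrawn early.** Under 9 or 12.2 the subject leaves the study. Under the section 6 and 7.4.2 schedules the next liver imaging would have been at the end of the intervention. Section 12.1 adds no efficacy measurement. Laboratory values taken before withdrawal exist, but no imaging after baseline is planned. Under 12.2 or 17.1 a pool volunteer takes the place. The end-of-period imaging therefore comes from original subjects who were not withdrawn, plus replacements who were not withdrawn either.

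**Step 2: the plan's own figure.** Section 13.2 gives 40 per group at 90% power and one-sided 2.5%, and the section 6 summary gives 20 per group. Neither can be reproduced, because no effect size or SD is stated. Solving the noncentral t for the effect detectable with 90% power gives 0.734 SD (40 per arm) and 1.052 SD (20 per arm). These serve only as a scale.

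**Step 3: illustration of the shift.** The protocol gives no withdrawal rates, so every rate and gap below is an assumption.

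Let p be the fraction of an arm withdrawn and g the amount, in SD, by which those subjects would have ended worse than those kept. The mean of all randomised is (1 - p) x kept mean + p x (kept mean + g) = kept mean + p x g, with higher values worse. The kept mean therefore looks better than the full-arm mean by p x g, and

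shift in the difference = p1 x g1 - p2 x g2, in favour of the arm with the larger product.

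- 10% v 5%, g = 0.5 in both arms: 0.050 - 0.025 = 0.025 SD
- 10% v 5%, g = 1: 0.10 - 0.05 = 0.05 SD
- 15% v 5%, g = 0.5: 0.075 - 0.025 = 0.05 SD
- 15% v 5%, g = 1: 0.15 - 0.05 = 0.10 SD
- equal p and equal g: 0

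**Step 4: effect on the false-positive risk.** Assume no true effect, SD 1, arms refilled to n, and replacements drawn from the same population under the same rule. The standard error is sqrt(2/n): 0.2236 for n = 40 and 0.3162 for n = 20. The noncentrality is shift / standard error. The probability of exceeding the upper 2.5% point of t (1.991 on 78 df, 2.024 on 38 df) is:

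| Shift (SD) | 40 per arm | 20 per arm |
|---|---|---|
| 0 | 2.5% | 2.5% |
| 0.025 | 3.2% | 3.0% |
| 0.05 | 4.1% | 3.6% |
| 0.10 | 6.5% | 4.9% |

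This is the chance of a significant result favouring the arm with more withdrawals. Against the detectable effect at 40 per arm, the largest shift is 0.10 / 0.734, about 14%, and the smallest is 0.025 / 0.734, about 3%.

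**The case against.** The strongest reply is that the protocol gives no reason to expect unequal withdrawal. Both arms take 450 mg of phosphatidylcholine and differ in formulation and 7 mg of lycopene. Section 12 calls adverse events very unlikely, and section 11 keeps out volunteers known to be intolerant of either ingredient. The same rule applied to both arms, with the same gaps, shifts nothing. This stands. It limits what can be said about size, but it does not supply the missing final scans. Withdrawal for poor adherence also does not depend on adverse events being common.

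Four stronger readings are tempting, and the document does not support them.

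- A reader might infer that the result will be biased in favour of the lycopene arm. Nothing in the protocol fixes a direction, or shows that withdrawal will differ by arm at all.
- A reader might infer that the final analysis is a completers-only comparison. Section 13 names no analysis set, and an analysis plan that is not shown may do so. What the protocol does fix is which subjects have a planned end-of-period measurement.
- A reader might infer that an unblinded principal investigator can steer withdrawals, since one sentence in section 6 tells that person the group assignments. Another sentence there says that no trial personnel are told, and sections 9 and 12.2 give the withdrawal decision to the Medical Officer. The blinding conflict is a separate matter.
- A reader might take the laboratory trigger literally and try to compute the resulting loss of effect. Any out-of-range value would then count. With ten independent tests and 95% reference ranges, 1 - 0.95^10 = 40% of healthy people would be flagged at a single visit. A rule that sweeping is hard to credit as intended, and the heading of 12.2 refers to adverse events. No one-cut-off model with a small withdrawal rate describes either that reading or the narrower 12.1 reading, so no figure is offered. This part is a wording fix.

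**Conclusion.** The concern holds in a bounded form. Sections 9 and 12.2 require withdrawal from the study, sections 12 and 17.1 allow it, and 12.2 and 17.1 replace those withdrawn. With imaging only at start and end and only safety follow-up stated, withdrawn subjects have no planned primary-endpoint measurement. That conclusion rests on the text alone and needs no assumed rate.

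The amount of bias is unknown and may be nil. The 0.025-0.10 SD range and the associated error rates rest entirely on the assumed 10-15% against 5% and gaps of 0.5-1 SD. They show a modest effect if withdrawal is unequal, and they are not a forecast. The point should be fixed because the loss cannot be repaired afterwards and prevention is cheap. It does not show that the trial's result would be invalid.

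**What to change.** Amend sections 9, 12, 12.2 and 17.1 to say that stopping the study product is not leaving the study. Every randomised subject keeps the visits already scheduled, including the final imaging, unless consent is withdrawn. Any volunteer added later is newly randomised and does not take the place of a withdrawn subject. The choice of analysis set can stay with the analysis plan.

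As a secondary wording change, limit the 12.2 laboratory trigger to findings that meet the section 12.1 adverse-event criteria, or to safety thresholds set by the clinical team.

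The cost is one protocol amendment, a few visits by subjects no longer taking the product, and slightly more variable data from including them. Those visits include the scheduled final CT, so its radiation exposure should be weighed openly.
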